Official title: Mindfulness-Based Intervention for Caregivers of Frail older adults:
Towards a model of intergenerational caregiving for Chinese families

NCT number: to be assigned

Document date: April 22, 2021

The research questions of the proposed study are:

- 1) investigate the effects of a brief mindfulness-based intervention for caregivers of frail elders in reducing caregiver burden and depression;
- 2) compare the effects of mindfulness-based intervention with an evidence-based caregiver programme; and
- 3) explore the factors that contribute to the positive improvements of both caregiver programmes, and develop a preliminary model for understanding and reducing caregiver burden and depression.

RESEARCH PLAN AND METHODOLOGY

Study design

In view of the research objectives about efficacy of the MBI and in the interest of developing a model of mediators in the MBI and intergenerational caregiving, a multi-site, three-arm, randomized controlled trial will be implemented (Baron et al., 2013). The effects of the MBI for caregivers for frail elderly will be tested by comparing the MBI (Arm 1), with psychoeducation (Arm 2), and treatment-as-usual (Arm 3). Assessments will be scheduled pre-intervention (T0), post-intervention (T1), and at 6-month follow-up (T2). The program effects will be tested using both pairwise between-subject comparisons (Arm 1 vs Arm 2, Arm 2 vs Arm 3, and Arm 1 vs Arm 3) and within-subject comparisons (measures at T0, T1, and T2). The between-group analyses will be adjusted for baseline scores and for factors related to outcomes, including the age and sex of the caregivers, the severity of depression, anxiety, caregiver burden, and the level of frailty of elderly. Refinement of design from a pilot study. A pilot study has been conducted in August to September 2019.

Sample size estimation. We calculated the sample size needed for the first two hypotheses and choose the larger one for the estimation of overall sample size. For the first hypothesis, the calculation is based on a previous study of an MBI for caregivers (Hou et al., 2014), in which an effect size of 0.64 in depression, with an estimation of an effect size of 0.14 for Arm 3. For a two-tailed α error of 5%, an 80% power, and a test of three independent groups, the required sample size will be 64 per arm (Cohen, 1988). For the second hypothesis, the calculation is based on a non-inferiority comparison was conducted. A non-inferiority margin of 50%, as common practice in non-inferiority trials (Althunian et al., 2017), is selected and the required sample size will be 51 per arm. We further adjust the sample size based on an estimation of drop-out rate and intra-class correlation. An estimation of a drop-out rate of 15% is based on two local studies of mindfulness-based intervention (Hou et al., 2014; Lo et al.,

2015). Besides, an estimation of intra-class correlations of 0.07 is based on PI's two recent mindfulness multi-site studies ranged from 0 to 0.07 (Lo et al., 2017; Lo et al., in press), and 240 caregivers will be recruited for this study. Based on such estimation, it should also be necessary to conduct mediational studies with .8 statistical power (Fritz & MacKinnon, 2007).

Recruitment of participants. The inclusion criteria for participation in this study are: 1) Caregivers of frail elderly based on a professional's assessment of Clinical Frailty Scale with a score of 6, indicating a moderate level of frailty or above (Rockwood et al., 2005). 2) Caregivers being adult children or children in-law of the elder care receiver. 3) Caregivers who are experiencing caregiver burden at the time of study, with scores of 8 or above in ZBI-4 (Bedard et al., 2001). The exclusion criteria include: 1) Caregivers who have diagnoses of psychosis, developmental disabilities, or cognitive impairment, which may present difficulties in comprehending the content of the program. 2) Spouses, siblings, or friends will be excluded as their burden or depressive symptoms may be attributed to different reasons. 3) Caregivers of elders with moderate to severe dementia will be excluded and the Clinical Dementia Rating Scale will be administered (Huges et al., 1982), and 4) Caregivers who had participated in a MBSR or equivalent.

The research project will be announced and promoted among collaborating NGOs and through advertisement in social media, promotional emails, and project leaflets. Four NGOs have indicated their intentions to contribute to this study by assisting in promotion, recruitment, program implementation and data collection. Support letters of these NGO collaborators have been provided in the appendix.

We will organize briefing sessions for explaining the rationale and procedures of the study half yearly. All interested caregivers will be screened using Clinical Frailty Scale, Clinical Dementia Rating Scale, and caregiver stress. Written consent will be collected for eligible participants. All NGO collaborators will provide standard care to the participants, including participants in Arm 3 who will not receive MBI nor psychoeducation before T2. The Research Assistant who is blinded to the personal data of the participants, will administer the random assignment using computer generated programming. Participants will be randomly assigned to MBI (Arm 1), psychoeducation (Arm 2), or treatment-as-usual (Arm 3). During the recruitment and implementation, both arm 1 and 2 are called "Family Psychoeducation Program", and the term "mindfulness" will not be used for Arm 1 to minimize the potential placebo effect. Cash remuneration coupons will be provided to caregivers who can complete the study at T1 and T2. A recruitment flowchart is attached in Appendix 1.

Procedures

Program planning and training. The themes and content of arms 1 and 2 are summarized in Appendix 2.

MBI (Arm 1). Based on the protocols of PI's previous clinical trials, brief mindfulness exercises will be integrated with psychoeducation of caregiving for frail elderly. The protocol for Arm 1 has been developed on mid-Sept, 2019 for the first pilot study.

Psychoeducation.

(Arm 2). The research team will modify START (STrAtegies for RelaTives) program for

caregivers of dementia (Livingstone et al., 2014) into a 10-hour group program. Major changes include the content originally related to the caregiving needs of dementia will changed to frail elderly. Two hours will be added to allow for more discussion of individual caregiver's concerns. The protocol for Arm 2 will be developed and a pilot study will be conducted shortly in early 2020. Arm 1 and 2 are parallel in program design. Both will be 4-session programs to be organized bi-weekly, and last for 10 hours in total. Both programs include 15-minute daily home practice assignments, with Arm 1 being guided with mindfulness exercises, and Arm 2 with coping and problem-solving skills. Both arms will be delivered in group format, with 10 to 15 caregivers in each group. Programs will be conducted in the service units of four NGO collaborators and PI's university. All instructors for Arm 1 require basic professional training in MBI, plus at least two-year experience in conducting MBI. Instructors for Arm 2 will be recruited from NGO with experience in working with caregivers of frail elderly for more than two years. Implementation and assessment.

After the pre-intervention assessment (T0), caregivers who meet inclusion criteria will be randomized into a MBI (Arm 1), psychoeducation (PSY, Arm 2), or treatment-as-usual (TAU, Arm 3). After the intervention programs, participants in three arms will complete the post-intervention assessment (T1). A 6-month follow up (T2) is offered as a booster and final assessment for arms 1 and 2. This study will be single-blinded and outcome assessors will be blinded to randomization status.

To ensure intervention fidelity, all program sessions will be audio-recorded and an independent rater will listen to 20% of the selected clips on random basis, and assess whether each element in the intervention protocol has been implemented with consistency. Higher concordance rates will signify greater fidelity to the intervention protocol, which will be carefully monitored throughout the study. The treatment fidelity of Arm 1 will be further assessed by Mindfulness-based Interventions-Teaching Assessment Criteria Scale (Crane et al., 2013). Those of Arm 2 will be assessed by a checklist for implementing START program.

Table 1. Outcome variables and measures

Study variables and measures	Validation in HK samples
Primary outcome variables	
Caregiver burden - Measured by 22-item Zarit Burden Interview (ZBI) (Zarit et al., 1980)	$\alpha = .88$ (Tang et al., 2017)
Secondary outcome variables	
Depressive symptoms - measured by 10-item The Center for Epidemiologic Studies Depression Scale (CES-D) (Radloff, 1977)	$\alpha = 0.78$ (Boey, 1999)
Anxiety symptoms - measured by 7-item Hospital Anxiety and Depression Scale – Anxiety subscale (HAD-A) (Zigmond & Snaith, 1983)	$\alpha = 0.77$ to 0.82 (Leung et al., 1999)
Positive caregiving experiences - Measured by 9-item Positive Aspects of Caregiving Scale (PAC) (Tarlow et al., 2004)	$\alpha = 0.89$ (Lou et al., 2015)
Spiritual well-being - measured by 12-item Functional Assessment of Chronic Illness Therapy–Spiritual Well-Being Scale (FACIT-Sp-12) (Peterman et al., 2002), with two subscales in meaning/peace and faith	$\alpha = 0.80$ (Wang, 2016)
Family conflicts - measured by 10-item Revised Conflict Tactics Scale (CTS2) (Beach et al., 2005), with subscales in psychological mistreatment (5 items) and physical abuse (5-items)	$\alpha = .81$ to $.82$ (Yan & Tang, 2001)
Biomarker: Heart rate variability - measured by the CorSense Heart Rate Variability monitor	N.A.
Mediators of outcome	
Cognitive factor: Coping styles - measured by 28-item brief COPE (Carver, 1997), with 11 subscales (problem-solving, accommodation, support-seeking, behavioral disengagement, denial, self-distraction, self-blame, humour, venting, substance use, and religion)	$\alpha = 0.76$ for whole scale, and $\alpha = .49$ to $.87$ for subscales (Tang et al., 2016)
Cognitive factor (psychoeducation-specific): Self efficacy - Measured by 5-item subscale of controlling upsetting thoughts (5 items) in the Revised Scale for Caregiving Self-Efficacy (RSCSE) (Steffen et al., 2002)	$\alpha = .86$ (Au et al., 2009)
Cognitive factor (mindfulness-specific): Experiential avoidance - measured by 15-item The Brief Experiential Avoidance (BEAQ) Questionnaire (Gamez et al., 2011)	$\alpha = 0.81$ (Lo et al., in review)

3. Data Analyses

[figure not shown]
All analyses will be carried out according to the intention-to-treat approach and all participants who receive randomization and allocation to one of three treatment arms will be included for analyses (Moher et al., 2010). Repeated measure ANOVA will be used to evaluate the effects of the MBI (Arm 1), relative to PSY (Arm 2) and TAU (Arm 3), and the analyses of the primary and secondary outcome measures will be analyzed. In addition to the immediate programme effects, outcomes measured at T1 and T2 will be compared, to assess whether maintenance effects will be sustained at 6-months.

The mediation effects on the relationships between group (MBI or PSY vs. TAU)

variables and caregiver outcome variables (ZBI, CES-D, HAD-A), controlling the baseline variables (sex and age of caregivers, frailty score), will be evaluated using the PROCESS macro in SPSS (Hayes, 2012), in order to compute the effect of the independent variable on the mediator (a), the effect of the mediator on the dependent variable (b), total effect (c), direct effect (c'), and bootstrapped (i.e., 10,000 random samples) bias-corrected 95% confidence intervals of the indirect effect (ab).

According to Hayes (2009), with significant paths a and b, even without a significant path c, confidence intervals that do not include zero indicate a significant indirect (i.e., mediation) effect.

Appendix 1
Recruitment Flowchart

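### ZBI is compared between three pairs of arms, with assessments at T1 and T2, but the plan names no primary contrast, time point, testing order or multiplicity rule

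*Combined protocol and SAP*

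**What the plan says.** - **Contrasts.** Study design plans "pairwise between-subject comparisons (Arm 1 vs Arm 2, Arm 2 vs Arm 3, and Arm 1 vs Arm 3", plus within-subject comparisons over T0, T1 and T2.
- **Outcome.** Table 1 lists the 22-item ZBI as the only primary outcome, with no time point attached.
- **Analysis.** 3. Data Analyses names a repeated-measures ANOVA of Arm 1 relative to Arms 2 and 3 and adds that "the analyses of the primary and secondary outcome measures will be analyzed". It does not name the deciding model term, give a level for any test, or say whether the pairwise comparisons depend on the ANOVA. It separates immediate effects from a T1-to-T2 comparison of maintenance, but calls neither primary.
- **Error rate.** The only one is in Sample size estimation: "For a two-tailed α error of 5%, an 80% power, and a test of three independent groups". That paragraph sizes a first hypothesis, with Arm 3 as comparator, from "an effect size of 0.64 in depression, with an estimation of an effect size of 0.14 for Arm 3", and concludes that "the required sample size will be 64 per arm". It sizes a second hypothesis as a non-inferiority comparison at 51 per arm. It takes the larger size and does not call either hypothesis primary.

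**The concern.** Three contrasts at two post-baseline time points make up to six between-arm comparisons of the primary outcome. A claim for the MBI could rest on Arm 1 vs Arm 2 or Arm 1 vs Arm 3, at T1 or at T2. With no decisive test named, the basis for success can be chosen after the results are seen, and nothing in the analysis section holds the 5% that the sample size assumes. The sample-size paragraph adds to the doubt: it describes a three-group test, while its figure is the size for one unadjusted two-group comparison.

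**Working it through.** **1. The plan's own figure.** The difference used is 0.64 − 0.14 = 0.50 SD, for depression. For two groups at two-sided 5% and 80% power, n = 2(1.960 + 0.842)² / 0.50² = 62.8, so 63 per arm. The t-test version gives 63.8, so 64. The stated 64 is reproduced as a single Arm 1 vs Arm 3 comparison.

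A three-group ANOVA at the same level and power would need 59 per arm if Arm 2 equals Arm 1, and 79 if Arm 2 lies midway between Arms 1 and 3. The words "a test of three independent groups, the required sample size will be 64 per arm" therefore do not describe the calculation behind the number.

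**2. Error with no true differences.** Inputs:
- 68 analysed per arm: 240 / 3 = 80, and 80 × 0.85 = 68 after the stated 15% drop-out. Equal allocation is assumed, as the ratio is not stated; 80 per arm gives almost the same results.
- Two-sided 5% t-tests with pooled variance. Applying 5% to every test is an assumption.
- The T1-T2 correlation of the scores analysed. The documents give none, so a range is shown.

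Simulated chance of at least one significant result (200,000 trials per setting):

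| T1-T2 correlation | All six, ungated | Four involving Arm 1, ungated | All six, three-group F test as gate at each time point |
|---|---|---|---|
| 0 | 22.6% | 17.1% | 9.7% |
| 0.5 | 21.3% | 16.2% | 9.2% |
| 0.7 | 19.5% | 14.9% | 8.5% |
| 0.8 | 18.3% | 13.9% | 7.8% |
| 1 | 12.2% | 9.0% | 5.0% |

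Three contrasts at one time point give about 12% ungated and 5% gated. Treating six tests as independent would give 1 − 0.95⁶ = 26.5%, which overstates the problem because the tests share arms and participants.

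**3. What control would cost.** With d = 0.50 and 68 per arm, ignoring clustering, power for Arm 1 vs Arm 3 is 82% when it is the first test in a fixed order. It is 69% with Bonferroni over three contrasts. By the formula in step 1, Bonferroni needs 2(2.394 + 0.842)² / 0.25 = 84 per arm for three contrasts and 2(2.638 + 0.842)² / 0.25 = 97 for six tests, before drop-out and clustering. A fixed order leaves 64 unchanged. These power figures only compare the options; the plan's own intra-class correlation of 0.07 would lower all of them.

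**The case against.** A reader might infer that the plan runs six tests, each at 5%, and so carries a 20% false-positive rate. The documents do not support that as a fact, for four reasons.

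- **No per-test level is stated.** The 5% comes from the sample-size section alone.
- **The ANOVA could act as a gate.** The text is silent on this. Gating at each time point gives about 8% to 10% for correlations of 0 to 0.8, and a single overall F test holds about 5% with no true differences. This stands as a limit on the size of the concern but does not remove it. If both programmes beat usual care by 0.5 SD and are equal to each other, the overall test is nearly always passed, and a false Arm 1 vs Arm 2 difference at T1 or T2 then appears in about 8% to 9% of trials (correlation 0.8 to 0.5).
- **Six is the maximum count.** Arm 2 vs Arm 3 cannot support a claim for the MBI, which leaves four comparisons. Arm 1 vs Arm 2 is sized as non-inferiority, and a finding of non-inferiority between equal arms is not an error. Against that, Study design and 3. Data Analyses carry no margin or non-inferiority test forward, so as written it reads as an ordinary comparison. It is also unclear whether Arm 3 is assessed at T2: Study design schedules T2 without distinction, the recruitment text withholds both programmes from Arm 3 until T2, and Implementation and assessment describes T2 as being for Arms 1 and 2.
- **The contrasts are not wholly unranked.** The sample-size section has a first and a second hypothesis. That is a basis for an order, but it is not stated as a testing rule.

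Nor does 64 per arm show adequate power for ZBI. The 0.50 is for depression, a secondary outcome, and no ZBI effect is given.

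**Conclusion.** The omission is real: there is no primary contrast, primary time point, testing order or multiplicity rule for ZBI. Its size depends on rules the plan leaves open. Ungated at 5%, the familywise error is about 12% to 23% for six comparisons (correlation 1 to 0), near 20% for an assumed 0.5 to 0.7, and about 14% to 16% for the four that could support an MBI claim (correlation 0.8 to 0.5). With an ANOVA gate it is about 5% to 10%. All these figures assume no true differences between arms, and 20% should not be quoted as the trial's error rate. The trial is sized for Arm 1 vs Arm 3 as one unadjusted comparison, and the plan should say so. It should be corrected because the gap leaves the winning comparison open to choice and is cheap to close.

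**What to change.** 1. Name ZBI at T1, Arm 1 vs Arm 3, as the single primary test at two-sided 5%. This is the contrast already sized, and the analysis section already treats T1 as the immediate effect.
2. If it succeeds, test in this prespecified order: Arm 1 vs Arm 2 as the second, non-inferiority hypothesis; Arm 2 vs Arm 3; then the T2 contrasts.
3. Before step 2 can be used, express "A non-inferiority margin of 50%, as common practice in non-inferiority trials" as a difference on the ZBI scale and state the one-sided level. The stated 51 per arm matches a 0.50 SD margin at one-sided 5% (t-test 50.2); at one-sided 2.5% the normal formula gives 63.
4. Reconcile the passages on whether Arm 3 is assessed at T2 before listing any T2 contrast that involves it.
5. In the phrase "an 80% power, and a test of three independent groups", replace the three-group description with a two-sample comparison of Arm 1 and Arm 3 at a standardised difference of 0.50. State that the 0.50 comes from depression and is assumed to carry over to ZBI.

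The cost is wording, plus the work of defining the margin and settling the T2 schedule. No extra participants are needed for the multiplicity control itself. Later comparisons are not confirmatory if an earlier one fails. Other orders after the first test are defensible, provided one is fixed before the data are seen.

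### Uncontrolled within-subject comparisons stand beside the between-arm comparisons as tests of programme effect, and the plan does not say which decides

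*Combined protocol and SAP*

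**What the plan says.** - **Tests of effect (Study design).** "The program effects will be tested using both pairwise between-subject comparisons" for the three pairs of arms, together with "within-subject comparisons (measures at T0, T1, and T2". Nothing ranks one kind above the other or calls the second descriptive.
- **Adjustment (Study design).** "The between-group analyses will be adjusted for baseline scores and for factors related to outcomes". Adjustment is stated for the between-group analyses only.
- **Entry (Recruitment of participants).** "Caregivers who are experiencing caregiver burden at the time of study, with scores of 8 or above in ZBI-4".
- **Primary outcome (Table 1).** "Caregiver burden - Measured by 22-item Zarit Burden Interview (ZBI", which measures the same construct as the entry screen. Depressive symptoms are a secondary outcome.
- **Treatment-as-usual (Sample size estimation).** An effect of 0.64 in depression for the mindfulness programme is set "with an estimation of an effect size of 0.14 for Arm 3".
- **Analysis (Data Analyses).** A repeated-measures ANOVA evaluates the mindfulness arm relative to the other two. The section names no deciding term and does not withdraw the within-subject tests. It adds that "outcomes measured at T1 and T2 will be compared, to assess whether maintenance effects will be sustained at 6-months".
- **Who has a T2.** Study design schedules T2 without excluding any arm, and the recruitment text has Arm 3 go without either programme until T2. The Implementation and assessment paragraph, however, describes T2 as a booster and last assessment for the two active arms.

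**The concern.** Randomisation protects a contrast between arms. It does nothing for a change over time within one arm, or for a time effect averaged over arms. Natural recovery, repeated measurement, standard care and regression to the mean all enter such a change and look like benefit.

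Regression to the mean is a particular possibility here, because caregivers enter on a high score on a short form of the primary outcome scale. If the within-subject result is read as a test of programme effect, an inactive programme has a good chance of appearing to work.

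Maintenance raises a related problem. A T1 to T2 comparison that does not involve the control arm cannot show that an advantage over control persisted. Control may have caught up, or the comparison may lack power.

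**Working it through.** **1. The plan's own figure.** The 64 per arm follows from 0.64 − 0.14 = 0.50. The normal formula gives n = 2(1.960 + 0.842)²/0.50² = 62.8, so 63; the t-test version gives 63.8, so 64. The figure is reproduced and is not in question. It shows that 0.14 is treated as an effect in the treatment-as-usual arm that is subtracted from 0.64. It does not show which SD scales it.

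**2. Inputs for the illustration.**
- From the plan: 240 recruited, 15% drop-out, two-sided 5%, 0.14 for Arm 3.
- Assumed: equal allocation, so 240/3 = 80 per arm and 80 × 0.85 = 68 analysed; pre-post correlation r of 0.5 to 0.8; 0.14 read as a pre-post change in baseline SD units.

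**3. Chance that an inactive arm is significant on one T0–T1 paired test.** The standardised change is dz = drift/√(2(1 − r)), and power comes from the noncentral t with n = 68. For drift 0.14, dz runs from 0.14/√1.0 = 0.140 (r = 0.5) to 0.14/√0.4 = 0.221 (r = 0.8).

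| Drift (SD) | r = 0.5 | r = 0.8 |
|---|---|---|
| 0 | 5% | 5% |
| 0.14 | 21% | 44% |
| 0.20 | 37% | 73% |
| 0.30 | 68% | 97% |

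For drift 0.14, the range is 20% to 41% with 64 per arm and 24% to 50% with 80. If 0.14 is already in SD-of-change units, dz = 0.14 and the answer is about 21% whatever r is. If a significant improvement at either T1 or T2 counts, simulation (2,000 runs, 68 per arm, drift 0.14) gives 33% at r = 0.5 and 59% at r = 0.8.

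**4. Regression to the mean on the ZBI.** Let c be the correlation of ZBI-4 with the 22-item ZBI on the same occasion, p the share of those screened who pass, and z the matching normal cut-off. If screening takes place at T0, the expected drop from T0 to T1 is (c − c × retest) × φ(z)/p, in SD units of the screened population. The documents give none of these inputs. Assume c = 0.85 to 0.92, retest = 0.6 to 0.8 and p = 30% to 70%.
- Smallest: 0.85 × 0.2 × 0.3477/0.70 = 0.08 SD.
- Largest: 0.92 × 0.4 × 0.3477/0.30 = 0.43 SD.

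If screening is on a separate, earlier occasion and the retest correlation is the same between all occasions, the screen predicts T0 and T1 equally well: (c × retest − c × retest) × φ(z)/p = 0. The range is therefore about 0 to about 0.4 SD.

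**5. The between-arm comparison under the same conditions.** Two identical inactive arms of 68 were simulated with no drift, with drift 0.14, with selection on the screen, and with both. The test of the difference in change was significant in 4% to 6% of runs in every setting, close to the nominal 5%.

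**The case against.** The strongest reply is that between-subject and within-subject are the usual names for the arm and time factors of a mixed ANOVA. The Data Analyses section evaluates the mindfulness arm relative to the other two, and the baseline-adjusted pairwise contrasts are already planned. The documents never mention a separate paired test in each arm. This reading is fair, but it does not remove the point: the time effect is as uncontrolled as a paired test, only group-by-time is protected, and the plan does not single that term out.

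Four stronger inferences are tempting and are not supported:
- **That the plan has a rule declaring a programme, or treatment-as-usual, effective on a within-subject result alone.** No success rule of any kind is stated.
- **That the plan predicts a 0.14 drift on the primary outcome.** The figure stands beside a depression effect, which is a secondary outcome here, and is not called a pre-post change.
- **That ZBI scores must fall after T0.** The timing of the ZBI-4 screen relative to T0 is not settled, and with earlier screening the expected drop from this source could be about zero.
- **That maintenance will be tested within one arm and a non-significant T1–T2 change taken as proof.** The sentence says neither. It simply leaves out the control arm.

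**Conclusion.** The point holds as a flaw in a stated analysis. Comparisons without a control are listed as tests of programme effect, level with the randomised ones, and nothing later in the plan subordinates them. This is true on either reading of within-subject.

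The size is illustrative. The 21% to 44% rests on 68 per arm, r of 0.5 to 0.8 and the pre-post reading of a figure given for depression. Regression to the mean of about 0 to 0.4 SD rests on assumed correlations and pass rates and on when screening takes place. The direction of the error needs none of these values: any improvement that is not due to the programme inflates the within-subject test and cancels in expectation between arms.

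The trial's design and its between-arm comparisons are not undermined on this point. What is at risk is how success and maintenance are judged and reported.

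**What to change.** 1. State in Study design and Data Analyses that all efficacy conclusions rest on the baseline-adjusted between-arm (group-by-time) contrasts at T1 and T2.
2. Report within-arm change descriptively, with no claim of programme effect attached to it.
3. Judge maintenance by the between-arm difference at T2 with its 95% CI. A T1–T2 comparison may be shown as description.
4. Confirm that Arm 3 is assessed at T2, and reconcile the Implementation and assessment wording with Study design and the recruitment text. A T2 contrast with treatment-as-usual depends on this.

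The cost is small. If Arm 3 has its T2 assessment, this is a change of wording that uses data and contrasts already planned. The price is fewer nominally significant within-arm results to report.

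### The 80% power and 64 per arm rest on a depression effect, so power for the only primary outcome, caregiver burden (ZBI), is not established

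*Combined protocol and SAP*

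**What the plan says.** **Sample size estimation.** Two calculations are made and the larger is carried forward. The first uses "an effect size of 0.64 in depression" from a previous study of a mindfulness intervention for caregivers, "with an estimation of an effect size of 0.14 for Arm 3". The error rates and design are given as "For a two-tailed α error of 5%, an 80% power, and a test of three independent groups", with a result of 64 per arm. The second is a non-inferiority calculation giving 51 per arm; it names no outcome. The depression-based 64 therefore sets the size. After allowance for 15% drop-out and an intra-class correlation (ICC) of 0.07, the target is 240 caregivers.

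**Table 1.** Under "Primary outcome variables" there is one entry: "Caregiver burden - Measured by 22-item Zarit Burden Interview (ZBI"). Under "Secondary outcome variables" the first entry is "Depressive symptoms - measured by 10-item The Center for Epidemiologic Studies Depression Scale (CES-D").

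**Research questions.** The first question concerns the effect of the intervention in "reducing caregiver burden and depression", so it names both outcomes together.

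**Study design.** Between-group analyses are to be adjusted for baseline scores and other covariates.

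**The concern.** A sample-size statement should show what the trial can detect on its primary outcome. Here the stated power belongs to an outcome that the plan itself ranks as secondary. No ZBI effect or SD enters the calculation, and nothing argues that burden should respond as strongly as depression.

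The stake is interpretation. If the ZBI comparison is null, readers will take it as coming from a trial with 80% power for a worthwhile effect on burden. No calculation in the plan supports that reading, and the plan names no burden difference against which a null result could be judged.

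**Working it through.** **1. Reproduce the plan's figure.** Inputs from Sample size estimation: effect 0.64 (Arm 1) and 0.14 (Arm 3), two-sided alpha 5%, power 80%.

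- Difference: d = 0.64 - 0.14 = 0.50 SD.
- A two-sample t-test at d = 0.50 needs 63.8 per arm, rounded up to **64**, which is the plan's figure. Power at 64 per arm is 80.1%.
- Alternatives do not match: d = 0.64 alone gives about 40 per arm, and a three-group one-way ANOVA gives 53, 59 or 79 per arm at f = 0.25, 0.236 or 0.204.

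The arithmetic is sound. The 80% is the power for a 0.50 SD difference between two arms, with the 0.50 taken from depression.

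**2. Power for ZBI under assumed effects.** The documents give no ZBI effect, so every d below is an assumption. Equal allocation is also assumed, since no ratio is stated: 240 / 3 = 80 per arm, and 80 x 0.85 = 68 analysed. Clustering is ignored in this step.

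For a comparison adjusted for a baseline score that has correlation r with the outcome, the residual SD is multiplied by sqrt(1 - r^2). The effective d is then d / sqrt(1 - r^2). The documents give no r; 0.5 and 0.6 are assumed, with factors 0.866 and 0.800.

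| Assumed ZBI effect (SD) | Power, unadjusted | Power, adjusted (r = 0.5 to 0.6) |
|---|---|---|
| 0.30 | 41% | 52-58% |
| 0.40 | 64% | 76-82% |
| 0.50 | 82% | 92-95% |

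**3. ZBI difference detectable at 80% power, with clustering.**

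- With 68 per arm, no clustering and no adjustment, the detectable difference is 0.484 SD.
- Design effect DE = 1 + (m - 1) x 0.07. For groups of 10, 1 + 9 x 0.07 = 1.63. For groups of 15, 1 + 14 x 0.07 = 1.98.
- Against treatment-as-usual, with only the group-delivered arm inflated: 0.484 x sqrt((DE + 1) / 2). This gives 0.484 x sqrt(1.315) = 0.555 and 0.484 x sqrt(1.49) = 0.591.
- Arm 1 vs Arm 2, with both arms inflated: 0.484 x sqrt(DE). This gives 0.484 x sqrt(1.63) = 0.618 and 0.484 x sqrt(1.98) = 0.681.
- Adjusted values multiply these by 0.866 (r = 0.5) or 0.800 (r = 0.6). Against treatment-as-usual the range is 0.555 x 0.800 = 0.444 to 0.591 x 0.866 = 0.512. For Arm 1 vs Arm 2 it is 0.618 x 0.800 = 0.494 to 0.681 x 0.866 = 0.590.

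| Comparison, ICC 0.07, groups of 10 to 15 | Unadjusted | Adjusted (r = 0.5 to 0.6) |
|---|---|---|
| Arm 1 or Arm 2 vs treatment-as-usual | about 0.55 to 0.59 | about 0.44 to 0.51 |
| Arm 1 vs Arm 2 | about 0.61 to 0.69 | about 0.49 to 0.59 |

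The table ranges are slightly wider at some ends than the hand figures, because they also cover the normal approximation and the t-test on effective sample sizes. At ICC 0 the unadjusted value is 0.484, and the adjusted range is 0.484 x 0.800 = 0.39 to 0.484 x 0.866 = 0.42.

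**The case against.** **Burden may respond as strongly as depression.** If the true ZBI difference is about 0.50 SD, the same 64 per arm gives 80% power by the plan's own method. This stands. A reader might infer that the trial is underpowered for burden, or that the 80% cannot apply to it. The documents support neither: they contain no ZBI effect from which a shortfall could be computed. What is missing is the justification.

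**The plan never says in terms that 80% applies to ZBI.** It ties the figure to a first hypothesis, and the first research question names burden and depression together. This also stands, and it limits the point to a gap in the plan rather than a false statement. It does not close the gap, because Table 1 makes burden alone primary. A reader might infer from the research question that both outcomes must be positive for success and that joint power is what matters. The plan has no such rule, so joint power is not part of this point.

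**The planned analysis is more efficient than an unadjusted t-test.** This is right, and it matters. At an assumed baseline correlation of 0.5 to 0.6, the unadjusted figures are clearly pessimistic, which is why both sets are shown. The plan claims no such gain and gives no correlation, so the adjusted figures are no better established than the others.

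**The clustering inputs are uncertain.** The plan's ICCs ranged from 0 to 0.07 in multi-site studies. It does not say whether they describe sites or intervention groups, and 0.07 is the top of the range. Step 3 also keeps full group sizes after drop-out; with 8.5 to 12.75 completers per group, the unadjusted values fall to about 0.55-0.58 against treatment-as-usual and 0.60-0.66 for Arm 1 vs Arm 2. No single detectable effect should therefore be prescribed. Whether 240 is enough for an ICC of 0.07 is a separate question.

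**Conclusion.** The point holds as a gap in justification. The calculation that sets the trial size is for depression at 0.50 SD, a secondary outcome. For ZBI burden, the only primary outcome, the plan states no effect, no SD and no proxy argument, so 80% power is not established.

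How much this matters depends on a ZBI effect that the documents do not give. Across assumed effects of 0.30 to 0.50 SD, power without clustering runs from 41% to 82% unadjusted and from 52% to 95% adjusted. These figures rest on equal allocation, 15% drop-out and, for the adjusted ones, a baseline correlation of 0.5 to 0.6. They show how sensitive the claim is to the missing input; they do not estimate the trial's actual power. The trial can proceed at its planned size, but the power statement should be made to match the primary outcome.

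**What to change.** Revise the sample-size paragraph in three respects.

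1. Say that the 64 per arm and 80% power refer to depression at a between-arm difference of 0.50 SD. The paragraph says only depression, so the figure should not be attributed to a particular scale unless the source study used it.
2. Add the ZBI difference detectable at 80% power with 240 caregivers, computed under the planned baseline-adjusted analysis, with 15% drop-out and across the plan's ICC range of 0 to 0.07. State the baseline correlation and cluster size used. Give the difference for each comparison with treatment-as-usual and for Arm 1 vs Arm 2, and in ZBI points if a ZBI SD is available (for example from the 2019 pilot, if ZBI was measured there).
3. Say why a ZBI difference of that size is a reasonable target, or why the depression effect is a fair stand-in for burden.

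The cost is one revised paragraph and a stated figure that may look less favourable. No extra enrolment and no change to trial procedures is needed.
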